### **Hypersensitivity reactions**

No hypersensitivity reactions to ocrelizumab were reported in the controlled clinical trials.

Hypersensitivity may be difficult to distinguish from IRRs in terms of symptoms. A hypersensitivity reaction may present during any infusion, although typically would not present during the first infusion. For subsequent infusions, more severe symptoms than previously experienced, or new severe symptoms, should prompt consideration of a potential hypersensitivity reaction. If a hypersensitivity reaction is suspected during infusion, the infusion must be stopped immediately and permanently. Patients with known IgE-mediated hypersensitivity to ocrelizumab must not be treated.

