#### **4.6.2 Study Treatment Discontinuation**

Patients must discontinue study treatment if they experience any of the following:

- Ongoing pregnancy or breastfeeding (in case of pregnancy, treatment should be interrupted, and the patient should be monitored for safety; however, the patient can be re-started with the treatment after the pregnancy and breastfeeding period. During pregnancy and breastfeeding, the patient will continue to come for the regular schedule visits as per protocol and will perform all assessments except MRI).
- Life-threatening IRR or serious hypersensitivity reaction
- Active hepatitis B infection
- PML
- Active tuberculosis, either new onset or reactivation

The primary reason for study treatment discontinuation should be documented on the appropriate eCRF. Patient discontinuing the study treatment prematurely will be further monitored in a safety follow-up (see [Section 3.1.4](#)).

Patients who discontinue study treatment prematurely will not be replaced.

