**Table 2 Guidelines for Management of Specific Adverse Events**

Event	Action to Be Taken
Mild to moderate IRR	

• If the event that a patient experiences is a mild to moderate IRR (e.g. headache), the infusion rate should be reduced to half the rate at the time of the event.

• This reduced rate should be maintained for at least 30 minutes. If tolerated, the infusion rate may then be increased according to the patient's initial infusion schedule.

Severe IRR (or complex of flushing, fever, and throat pain)	

• If a patient experiences a severe IRR or a complex of flushing, fever, and throat pain symptoms, the infusion should be interrupted immediately, and the patient should receive symptomatic treatment.

• The infusion should be re-started only after all symptoms have resolved.

• The initial infusion rate at restart should be half of the infusion rate at the time of onset of the reaction.

Life-threatening or disabling IRR (e.g., anaphylaxis)	

• Immediately stop ocrelizumab if there are signs of a life-threatening or disabling IRR during an infusion, such as acute hypersensitivity or acute respiratory distress syndrome.

• The patient should receive appropriate treatment.

• Permanently discontinue ocrelizumab in these patients.

hr=hour; IRR=infusion-related reaction

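### Protocol 3.1.3, 4.6.2, 5.1.1.2 and Table 2 do not agree on what follows a suspected hypersensitivity reaction or a life-threatening infusion reaction

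*Protocol*

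**What the plan says.** Four places in the protocol bear on this.

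- **5.1.1.2, Hypersensitivity reactions.** The text warns that "Hypersensitivity may be difficult to distinguish from IRRs in terms of symptoms". It adds: "For subsequent infusions, more severe symptoms than previously experienced, or new severe symptoms, should prompt consideration of a potential hypersensitivity reaction". The action is then stated: "If a hypersensitivity reaction is suspected during infusion, the infusion must be stopped immediately and permanently". The section closes by barring treatment of patients with known IgE-mediated hypersensitivity to the drug.
- **4.6.2, Study Treatment Discontinuation.** The list of events that oblige a patient to stop study treatment includes "Life-threatening IRR or serious hypersensitivity reaction".
- **5.1.4, Table 2.** For a severe infusion-related reaction (IRR), the infusion is interrupted and symptoms are treated. Then: "The infusion should be re-started only after all symptoms have resolved", at half the rate in use at onset. For the life-threatening or disabling category the table says: "Immediately stop ocrelizumab if there are signs of a life-threatening or disabling IRR during an infusion, such as acute hypersensitivity" (acute respiratory distress syndrome is the other example). It continues: "Permanently discontinue ocrelizumab in these patients".
- **3.1.3, Criteria for Re-Treatment.** The checklist before each further dose includes a life-threatening (CTCAE Grade 4) infusion-related event at a previous infusion. The stated consequence is to pause dosing until the condition has resolved, or to withhold it with no end date. Hypersensitivity is not on the list.

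**The concern.** Sites need to know two things when an infusion reaction may be hypersensitivity: what to do with the infusion that is running, and whether the patient may be dosed again. The four places use different triggers: suspected, serious, life-threatening or disabling, and Grade 4. They also act on different objects: the infusion, study treatment, the drug, and the next dose. Nothing says how they fit together.

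Section 5.1.1.2 itself says that the two kinds of reaction are hard to tell apart, so the same event can plausibly be read under more than one rule. At stake is whether two sites facing the same event would handle the current infusion and the later doses alike.

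**Working it through.** No arithmetic applies. The check sets the current texts side by side and follows three cases through them.

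| Place | Trigger | Action | Acts on |
|---|---|---|---|
| 5.1.1.2 | Hypersensitivity suspected during infusion, any severity | Stop at once and for good | The infusion |
| 4.6.2 | Life-threatening IRR, or serious hypersensitivity | Mandatory discontinuation | Study treatment |
| Table 2, severe row | Severe IRR | Interrupt, treat, restart at half rate after resolution | The infusion |
| Table 2, life-threatening or disabling row | Such signs, with acute hypersensitivity as an example | Stop at once, discontinue permanently | The drug |
| 3.1.3 | Grade 4 infusion-related event at an earlier infusion | Pause until resolved, or withhold without limit | The next dose |

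**Case A: suspected hypersensitivity that is not serious.** Section 5.1.1.2 ends the infusion permanently. Section 4.6.2 does not list the event as a reason to discontinue treatment. Table 2 has no row for it unless it counts as acute hypersensitivity. Section 3.1.3 does not name it. Whether the patient may receive the next dose is therefore not stated. The case is a real category in this protocol, because 5.2.2 says that severity and seriousness are separate assessments.

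**Case B: new or more severe symptoms, graded severe, at a later infusion.** The severe row of Table 2 allows a restart and does not separate the first infusion from later ones. For that same symptom pattern, 5.1.1.2 says that hypersensitivity should be considered and, if it is suspected, that the infusion must not resume. Table 2 does not refer to that step. A site working from the table alone would not meet it, and the notes to Table 1 send sites to 5.1.4 for interruption and discontinuation.

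**Case C: Grade 4 infusion-related event.** Table 2 says that the drug is discontinued permanently, and 4.6.2 makes discontinuation mandatory. The one restart that 4.6.2 describes is after pregnancy and breastfeeding. Section 3.1.3 offers two outcomes for the same event. Withholding without limit fits the other two sections; pausing until resolution does not.

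**Does another section settle it?** The text of 5.1.4 announces further guidance in subsections, but section 5.2 follows directly after Table 2. For PML, 5.1.1.2 separates the action on suspicion from the action on confirmation. For hypersensitivity it makes no such distinction.

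**The case against.** The strongest reply is that the sections govern different actions and can be read in sequence. Section 5.1.1.2 concerns the infusion that is running; 4.6.2 concerns the whole course of treatment. A low threshold for the one and a higher threshold for the other can coexist. At a later infusion the investigator first considers hypersensitivity, stops if it is suspected, and otherwise manages the event as an IRR under Table 2.

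Other text narrows the gap. Table 2 can be read as placing every acute hypersensitivity reaction in its permanent-discontinuation row. Known IgE-mediated hypersensitivity bars treatment. Section 3.1.3 has a general item for significant or uncontrolled medical conditions. Section 5.2.2 lets the investigator call an event serious on medical judgment, and 4.6.1 lets the investigator withdraw a patient.

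Much of this stands. A reader might infer that the protocol gives two flatly opposite orders for a severe reaction at a later infusion. The documents do not support that. The wording in 5.1.1.2 is that such symptoms prompt consideration, which is a step short of suspicion, and only suspicion triggers the stop. Nor does Table 2 tell sites to re-expose a patient in whom hypersensitivity is suspected.

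The reply does not remove the problem, however. The sequence has to be supplied by the reader, because Table 2 does not state it. The consequence of 5.1.1.2 for later doses remains unstated, and investigator discretion does not make the written rules agree. The Grade 4 conflict between 3.1.3 and the other two places is untouched by the sequential reading.

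**Conclusion.** The instructions do not agree and should be reconciled. The clearest disagreements are three:

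- suspicion in 5.1.1.2 against seriousness in 4.6.2, with later doses left open;
- the missing link between the severe row of Table 2 and the warning in 5.1.1.2;
- the Grade 4 event, where 3.1.3 permits a pause and 4.6.2 and Table 2 require discontinuation.

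This is an inconsistency in a patient-safety instruction. It is moderate in weight and cheap to correct. The conclusion rests on the wording alone and assumes only that sites follow the text as written.

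No number of affected patients can be given. A reader might start from the 34.3% of ocrelizumab patients with IRRs in the pooled RMS trials (Protocol 1.2), but that figure covers all IRRs, and 5.1.1.1 says that they were reported more often at the first infusion. It does not measure new or more severe reactions at later infusions. Section 5.1.1.2 reports no hypersensitivity reactions in the controlled trials.

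A reader might also infer an effect on the primary result, because SAP 4.4.1 excludes event-free patients who discontinue for reasons other than death or lack of efficacy. The documents give no rate from which such an effect could be calculated, and none is claimed.

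**What to change.** The sponsor should reconcile 3.1.3, 4.6.2, 5.1.1.2 and Table 2 so that they give consistent instructions, both for the infusion in progress and for later doses. That includes the outcome after a Grade 4 infusion-related event. Table 2 should carry a cross-reference to the hypersensitivity text in 5.1.1.2. Which clinical rule applies is for the sponsor to decide, and no rule is proposed here.

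The cost is a protocol clarification and a letter to sites. It needs no new data, visits or analyses.

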### **Malignancies including Breast Cancer**

Patients should follow standard breast cancer screening guidelines.

Please see the IB for more details.

### **Neutropenia**

In the controlled treatment period, decreased neutrophils were observed in 12 to 15% of MS patients treated with ocrelizumab, in PPMS and RMS respectively. Most were mild to moderate in severity, and approximately 1% of the patients had Grade 3 or 4 neutropenia; no temporal association with infections was identified. Based on additional patient exposure, an association between neutropenia and serious infections with ocrelizumab treatment was not observed.

Additional information can be found in the current IB.

#### **5.1.2 Risks Associated with Corticosteroids**

The adverse reactions of corticosteroids may result from unwanted glucocorticoid actions, or from inhibition of the hypothalamic-pituitary-adrenal axis. Please refer to local Prescribing Information.

#### **5.1.3 Risks Associated with Antihistamines**

The adverse reactions depend on the sedating properties of the antihistamine and include but are not limited to nausea, drowsiness, headaches, dry mouth, and allergic reactions such as rash. Please refer to local Prescribing Information.

### 5.1.4 Management of Patients Who Experience Specific Adverse Events

Guidelines for management of specific adverse events are outlined in [Table 2](#).

Additional guidelines are provided in the subsections below.

**Table 2 Guidelines for Management of Specific Adverse Events**

Event	Action to Be Taken
Mild to moderate IRR	

• If the event that a patient experiences is a mild to moderate IRR (e.g. headache), the infusion rate should be reduced to half the rate at the time of the event.

• This reduced rate should be maintained for at least 30 minutes. If tolerated, the infusion rate may then be increased according to the patient's initial infusion schedule.

Severe IRR (or complex of flushing, fever, and throat pain)	

• If a patient experiences a severe IRR or a complex of flushing, fever, and throat pain symptoms, the infusion should be interrupted immediately, and the patient should receive symptomatic treatment.

• The infusion should be re-started only after all symptoms have resolved.

• The initial infusion rate at restart should be half of the infusion rate at the time of onset of the reaction.

Life-threatening or disabling IRR (e.g., anaphylaxis)	

• Immediately stop ocrelizumab if there are signs of a life-threatening or disabling IRR during an infusion, such as acute hypersensitivity or acute respiratory distress syndrome.

• The patient should receive appropriate treatment.

• Permanently discontinue ocrelizumab in these patients.

hr=hour; IRR=infusion-related reaction

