### **5.3.3 Assessment of Severity of Adverse Events**

The adverse event severity grading scale for the NCI CTCAE (v4.0) will be used for assessing adverse event severity. Table 3 will be used for assessing severity for infusion related reactions and adverse events that are not specifically listed in the NCI CTCAE.

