**Table 3 Adverse Event Severity Grading Scale for IRRs and Other Events Not Specifically Listed in NCI CTCAE**

Grade	Severity
1	Mild; asymptomatic or mild symptoms; clinical or diagnostic observations only; or intervention not indicated
2	Moderate; minimal, local, or non-invasive intervention indicated; or limiting age-appropriate instrumental activities of daily living a
3	Severe or medically significant, but not immediately life-threatening; hospitalization or prolongation of hospitalization indicated; disabling; or limiting self-care activities of daily living b,c
4	Life-threatening consequences or urgent intervention indicated d
5	Death related to adverse event d

NCI CTCAE = National Cancer Institute Common Terminology Criteria for Adverse Events.

Note: Based on the most recent version of NCI CTCAE (v4.0), which can be found at: [http://ctep.cancer.gov/protocolDevelopment/electronic\\_applications/ctc.htm](http://ctep.cancer.gov/protocolDevelopment/electronic_applications/ctc.htm)

- a Instrumental activities of daily living refer to preparing meals, shopping for groceries or clothes, using the telephone, managing money, etc.
- b Examples of self-care activities of daily living include bathing, dressing and undressing, feeding oneself, using the toilet, and taking medications, as performed by patients who are not bedridden.
- c If an event is assessed as a "significant medical event," it must be reported as a serious adverse event (see Section 5.4.2 for reporting instructions), per the definition of serious adverse event in Section 5.2.2.
- d Grade 4 and 5 events must be reported as serious adverse events (see Section 5.4.2 for reporting instructions), per the definition of serious adverse event in Section 5.2.2

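### The trigger for permanently stopping ocrelizumab after an infusion reaction is not the same in Table 2, Table 3, Section 4.6.2 and the re-treatment criteria

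*Protocol*

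**What the plan says.** Four places in the protocol bear on what happens after an IRR.

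- **Table 2 (Section 5.1.4)** has three rows, described in words and without grades. For a severe IRR the infusion is interrupted, and "The infusion should be re-started only after all symptoms have resolved", at half the rate in force when the reaction began. For a life-threatening or disabling IRR the instruction is "Immediately stop ocrelizumab if there are signs of a life-threatening or disabling IRR during an infusion", followed by "Permanently discontinue ocrelizumab in these patients".
- **Section 5.3.3 and Table 3** set the severity scale: "Table 3 will be used for assessing severity for infusion related reactions". Grade 3 reads "Severe or medically significant, but not immediately life-threatening; hospitalization or prolongation of hospitalization indicated; disabling". Grade 4, the life-threatening grade, does not use the word *disabling*.
- **Section 4.6.2**, the list of events that oblige a patient to discontinue study treatment, has one entry for infusion reactions: "Life-threatening IRR or serious hypersensitivity reaction".
- **Section 3.1.3, Criteria for Re-Treatment with Ocrelizumab**, lists only a life-threatening, CTCAE Grade 4 infusion event at an earlier infusion. Its consequence is that dosing is put on hold, either until the condition resolves or with no end date.

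**The concern.** *Severe* and *disabling* lead to different outcomes in Table 2, yet the scale that the protocol prescribes for IRRs puts the second inside the first. A site that grades a disabling, non-life-threatening reaction by Table 3 arrives at Severe, which is the restart row. A site that matches the word *disabling* to Table 2 arrives at permanent discontinuation. The two other lists that control further dosing do not settle it, because neither contains a disabling IRR.

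At stake is whether a patient is re-exposed after such a reaction or never treated again, in an open-label, multicentre study where the decision is made during the infusion. The protocol's Section 5.1 itself counts the treatment interruption criteria among the means of keeping patients safe. Uneven practice would also show, in a small way, in the SAP's tables of adverse events leading to drug discontinuation (SAP Section 4.6.2).

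**Working it through.** No arithmetic underlies the inconsistency, so the check sets the texts side by side.

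**Step 1. Map Table 2 to Table 3 by wording.**

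| Table 2 row | Matching Table 3 grade | Later dosing under Table 2 |
|---|---|---|
| Mild to moderate | 1 and 2 | Continue at reduced rate |
| Severe | 3, which includes *disabling* | Restart after resolution |
| Life-threatening or disabling | 4, plus the *disabling* part of 3 | Permanent discontinuation |

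The second and third rows overlap in one category only: an IRR that is disabling but not life-threatening. A life-threatening IRR belongs to the third row alone. A Grade 3 IRR that is not disabling belongs to the second row alone.

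**Step 2. Look for a tie-break.** Table 2 states no precedence between rows. Section 5.1.4 announces further guidelines in subsections below, but none follow the table; the next heading is Section 5.2.

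**Step 3. Compare the triggers in the three places that govern further dosing.**

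| Place | Life-threatening IRR | Disabling, not life-threatening IRR |
|---|---|---|
| Table 2 | Permanent stop | Permanent stop and restart both match |
| Section 4.6.2 | Mandatory discontinuation | Not listed, unless it is also a serious hypersensitivity reaction |
| Section 3.1.3, re-treatment | Hold until resolved, or indefinitely | Not listed |

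The middle column shows a second mismatch that needs no reference to Table 3. For a life-threatening IRR, Table 2 and Section 4.6.2 end treatment, while the re-treatment criteria leave open a hold that lifts on resolution.

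**Step 4. Size.** Section 1.2 gives 34.3% of ocrelizumab patients with any IRR in the pooled relapsing-MS Phase III studies: 0.343 × 750 = 257 patients if that rate applied here. This counts all IRRs and says nothing about disabling ones. The nearest figures concern serious IRRs, which is a different property from Grade 3. They are one ocrelizumab patient in the relapsing-MS studies, with a Grade 4 reaction, and 5 patients (1.0%) in the primary progressive study, with grades not given. The overlap category has no rate in the documents.

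**Step 5. Reach into the primary analysis.** Under SAP Section 4.4.1, a patient who stops before Week 96 for a reason other than death or lack of efficacy, with no disease activity so far, is excluded. At the planned rate, 30% of 750 is 225 patients with NEDA. Excluding one patient who would have had NEDA gives 224/749 = 29.9%. Excluding one who would not gives 225/749 = 30.04%. The shift is at most about 0.1 percentage point per patient, against the plan's 95% CI half-width of 3.3 points.

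**The case against.** The strongest reply is that Table 2 stands alone. It uses no grades and does not cite Table 3, which sits in the part of the protocol about capturing and grading adverse events. For treatment action, the text under Table 1 (Section 4.3.2.1) points to Section 5.1.4. There a disabling IRR is named once, with one outcome. On that reading the specific word prevails over the general one, and a site that restarted would be overlooking the row that names its patient's reaction. The examples also separate the rows: flushing, fever and throat pain in one; anaphylaxis, acute hypersensitivity and acute respiratory distress syndrome in the other. Section 5.1.1.2 separately requires a permanent stop of the infusion when hypersensitivity is suspected. And because seriousness in Section 5.2.2 includes lasting or significant disability, the serious-hypersensitivity entry in Section 4.6.2 already covers some disabling reactions.

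Much of this stands, and it narrows the point. A reader might infer that two sites could each follow the protocol exactly and act in opposite ways on the same day. That goes too far: both rows halt the infusion at once, the text gives no time for a restart, and a specific-row reading is available. A reader might also take Section 4.6.2 to name life-threatening IRRs alone, but it names serious hypersensitivity too.

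What the reply does not explain is why the disabling trigger, if Table 2 intends it to control, is missing from both the mandatory stop list and the re-treatment criteria. Nor does it touch the difference between a permanent stop and a hold after a Grade 4 reaction. The precedence it relies on is reasonable but unwritten.

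**Conclusion.** The inconsistency is real and narrow. It covers IRRs that are disabling but neither life-threatening nor a serious hypersensitivity reaction, together with the differing consequence for a Grade 4 reaction in Section 3.1.3. The first part rests on linking Table 2 to Table 3 through Section 5.3.3; the second is visible on the face of the texts.

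The number of patients affected cannot be estimated from the documents. It is probably very small and could be zero. A reader might assume that 1–3% of patients have a Grade 3 IRR and arrive at 8 to 23 of 750 (0.01 × 750 = 7.5; 0.03 × 750 = 22.5). The documents do not support using that as the size: they give no Grade 3 IRR rate, and Grade 3 reactions that are not disabling fall in one row only.

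A reader might also infer a threat to the primary NEDA result, since stopping treatment can remove a patient from that analysis. At about 0.1 percentage point per patient and a count near zero, the effect is negligible. The point rests on patient safety and uniform conduct. It takes no position on which action is right.

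**What to change.** Reconcile Table 2, Table 3, Section 4.6.2 and the re-treatment criteria in Section 3.1.3, so that every IRR falls in exactly one Table 2 row. Two ways of drafting this are to key the rows to Table 3 grades, or to keep the words and state where *disabling* belongs. Then use one form of words for the permanent-stop trigger and its consequence in Table 2, Section 4.6.2 and Section 3.1.3. The sponsor decides which action attaches to which reaction.

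The cost is a wording change to the tables and the two lists in the next amendment, with a letter to sites. It needs no new data and no change to the SAP.
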